- ^p IFN- γ ELISpot: Following AT132 administration, in cases of clinically important elevated bilirubin, elevated aminotransferases, elevated troponins, and/or elevated creatine phosphokinase that in the Investigator's judgment may be related to T-cell responses, repeat IFN- γ ELISpot response testing is suggested. Appropriate care for an individual subject will be determined by the Investigator based on an assessment of the subject's overall medical status.
- ^q The sample will only need to be collected 1 time during the study. The sample will be collected at the Week 12 visit, unless HLA type has been obtained in INCEPTUS. For subjects in Part 1 who have already passed the timepoint listed above, the HLA sample will be collected at the Week 48 visit or the Month 24 visit, whichever occurs first.
- ^r If a subject has discontinued the use of the ventilator and has 2 assessments with the MIP at 80 cmH₂O, testing for MIP, MEP, and P0.1 can be stopped.

- ^s The site pulmonologist and local pulmonologist, if applicable, will review the results from the visit, assess the subject, determine if the subject meets the criteria outlined in [Table 1](#) to begin reduction of hours on the ventilator, and determine if the subject meets the criteria outlined in [Table 2](#) to discontinue the ventilator.
- ^t Daytime polysomnogram not required at Week 48 if subject has already been weaned off the ventilator.
- ^u The severity of secretions and burden of secretions management will be assessed using the PGIS-S and PGIS-I ([Appendix 3](#)). The same parent/LAR/caregiver should report throughout the study (whenever possible).
- ^v All physical therapy assessments should be videoed and performed according to the site manual.
- ^w If a subject has a total score of 56 for 2 consecutive assessments, the CHOP INTEND will not be required for future visits.
- ^x The PedsQL is to be performed for all subjects, regardless of age. Subjects < 2 years of age should be administered the version for 2- to 4-year-olds.
- ^y See [Appendix 5](#).
- ^z In-depth interviews are optional and will be completed at either Week 24 or Week 48.
- ^{aa} Parents/LARs/caregivers (the same person every time, whenever possible) in ASPIRO will be asked to complete forms for subjects 8 months and older.
- ^{bb} Subjects will be administered a course of glucocorticoid therapy commencing Day -1 and continuing for a period of 16 weeks as a preventative measure for immune-mediated hepatic injury. For subjects weighing < 60 kg, the dose will be 1 mg/kg prednisolone orally daily for 8 weeks, then tapered down for 8 weeks per Investigator discretion. For subjects weighing ≥ 60 kg, the dose will be 60 mg prednisolone orally daily for 8 weeks, then tapered down for 8 weeks per Investigator discretion.
- ^{cc} Ursodiol to be dosed at 20 mg/kg/day (divided either BID or TID at the Investigator's discretion) to Week 12 and at the Investigator's discretion thereafter.
- ^{dd} Viral shedding will be assessed on samples of saliva (swab), stool, and urine (diaper collection or urine bag). Collection of each sample type will begin on Day 1 and will continue until each sample type has 3 consecutive data points at or below the limit of detection (BLOD). Sponsor will notify site when collection can cease. Not conducted at Week 10 or 14.
- ^{ee} Subjects in Germany will not have a wrist X-ray. After the Week 48 visit, wrist X-ray only needs to be performed annually thereafter (Month 24, Month 36). As of protocol v12, the wrist X-ray assessment will no longer be collected at Month 48 visit onward.
- ^{ff} As of protocol v12, these assessments will no longer be collected at Month 48 visit onward.

5.6 Schedule of Events for Subjects Treated with AT132: Month 72 (Year 6) – Month 120 (Year 10) (End of Study)

Study Phase/Visit	Month 72	Month 84	Month 96	Month 108	Month 120
Study Day	2190	2555	2920	3285	3650
Visit Window (days)	±60	±60	±60	±60	±60
Physical Examination ^a	X	X	X	X	X
Ventilator Dependence Questionnaire ^b	X	X	X	X	X
Samples for:	X	X	X	X	X
Safety labs (hematology) (central lab) ^{c,d}	X	X	X	X	X
Safety labs (chemistry) (central lab) ^{d,e,f,g} Comprehensive metabolic profile ALT, AST, Total and direct bilirubin, GGT Serum bile acids, total (fasting preferred) PTT and PT/INR Troponin I and T CK Alpha fetoprotein	X	X	X	X	X
Liver ultrasound (local) ^f	X	X	X	X	X
Motor milestone assessments ^h	X	X	X	X	X
ACEND	X	X	X	X	X
Clinical global impression scales ⁱ	X	X	X	X	X
Swallowing questionnaire	X	X	X	X	X
Secretions management assessment ^j	X	X	X	X	X
AEs/concomitant medications	X	X	X	X	X

NOTE: Long-term follow-up visits and/or assessments after the 5-year (Month 60) visit can be done remotely per discretion of investigator in consultation with Medical Monitor.

AEs = adverse events; ACEND = Assessment of Caregiver Experience with Neuromuscular Disease; ALT = alanine aminotransferase; AST = aspartate aminotransferase; CK = creatine kinase; GGT = gamma-glutamyltransferase; INR = international normalized ratio; LAR = legally authorized representative; PGIS-I = Parental Global Impression of Secretion Improvement; PGIS-S = Parental Global Impression of Secretion Severity; PT = prothrombin time; PTT = partial thromboplastin time.

^a Complete physical examination with detailed neurological evaluation and respiratory function assessment will be conducted. It can be done remotely per discretion of investigator in consultation with Medical Monitor. When visit is done remotely, an abbreviated physical examination is acceptable.

^b After the daily diary has been stopped or after subject has completed Week 48, the parent/LAR/caregiver will complete the ventilator dependence questionnaire at clinic and contact visits through Year 10 (Month 120).

- ^c See [Appendix 1](#) for list of laboratory assessments.
- ^d The local laboratory can be used for visits, if needed (for example, the local laboratory can accommodate the analysis with a smaller amount of blood) or if the local laboratory does not accommodate the appropriate analysis, the central laboratory may be used.
- ^e See [Section 4.6.1](#) for details related to the evaluation of cardiac enzymes; monitoring, diagnosis, and treatment of myocarditis; and the role of the site pediatric cardiologist.
- ^f See [Section 4.6.2](#) for details related to the monitoring, diagnosis, and treatment of hepatobiliary toxicity and the role of the site hepatologist.
- ^g See [Section 4.6.3](#) for details related to the monitoring, diagnosis, and treatment of neuromuscular abnormalities.
- ^h All physical therapy assessments should be videoed and performed according to the site manual.
- ⁱ See [Appendix 5](#).
- ^j The severity of secretions and burden of secretions management will be assessed using the PGIS-S and PGIS-I ([Appendix 3](#)). The same parent/LAR/caregiver should report throughout the study (whenever possible).

5.7 Schedule of Events for Control Subjects: Control Baseline – Control Month 30 (End of Study)

Study Phase/Visit	Daily	Baseline	Week 4	Week 12	Week 16	Week 24	Week 36	Week 48, Months 15, 18, 21, 24, 30, or EW
Study Day(s)	NA	-2 to -1	28	84	112	168	252	336, 420, 504, 588, 672, 840
Visit Window (days)	-1	-1	±3	±3	±3	±14	±3	±3
Inclusion/exclusion criteria		X ^a						
Medical history		X ^b						
Physical examination ^c		X ^b	X	X	X	X	X	X
Vital signs ^d		X ^b	X	X	X	X	X	X
12-Lead ECG ^e		X	X	X	X	X	X	X
ECHO ^e		X	X	X	X	X	X	X
Growth parameters		X	X	X	X	X	X	X
Tanner stage (puberty assessment)		X						
Samples for:								
Safety labs (hematology) (central lab) ^{f,g}		X	X	X	X	X	X	X
Safety labs (chemistry) (central lab) ^{f,g,h,i}		X	X	X	X	X	X	X
Troponin T and/or I (central lab) ^{f,h}		X	X	X	X	X	X	X
Coagulation parameters (central lab) ^{f,g}		X	X	X	X	X	X	X
Anti-AAV8 antibody NAb and TAb (central lab)			X	X	X	X	X	X
Urinalysis (local lab) ^{f,g}		X	X	X	X	X	X	X
Liver ultrasound ⁱ		X	X	X	X	X	X	X
Bone age (wrist X-ray) (not applicable for Germany) ^j		X						
Diary of ventilator dependence ^k	X							
Ventilator Weaning and Discontinuation Assessment ^l		X	X	X	X	X		W48, Months 18, 24, 30 or EW
Assessment of ventilator parameters		X	X	X	X	X	X	X
MIP, MEP, P0.1, tidal volume		X	X	X	X	X	X	X

Study Phase/Visit	Daily	Baseline	Week 4	Week 12	Week 16	Week 24	Week 36	Week 48, Months 15, 18, 21, 24, 30, or EW
Study Day(s)	NA	-2 to -1	28	84	112	168	252	336, 420, 504, 588, 672, 840
Visit Window (days)	-1	-1	±3	±3	±3	±14	±3	±3
Secretions management assessment ^m		X ⁿ	X	X	X	X	X	X
Daytime polysomnogram						X		
Motor development milestone assessments ^o		X	X	X	X	X	X	X
Bayley-III, motor domain ^o		X	X	X	X	X	X	X
CHOP INTEND ^o		X	X	X	X	X	X	X
MFM-32 ^o		X	X	X	X	X	X	X
ACEND		X	X	X	X	X	X	X
PedsQL ^p		X	X	X	X	X	X	X
Clinical global impression scales ^q		X ^q	X	X	X	X	X	X
Swallowing questionnaire		X	X	X	X	X	X	X
Speech questionnaire		X	X	X	X	X	X	X
Communicative Development Inventories ^r		X	X	X	X	X	X	X
AEs/concomitant medications		X	X	X	X	X	X	X

AEs = adverse events; ACEND = Assessment of Caregiver Experience with Neuromuscular Disease; anti-AAV8 = anti-adenovirus 8; CGI-S = Clinical Global Impression of Severity; CHOP INTEND = Children's Hospital of Philadelphia Infant Test of Neuromuscular Disorders; ECG = electrocardiogram; ECHO = echocardiogram; EW = early withdrawal; LAR = legally authorized representative; MEP = maximal expiratory pressure; MFM-32 = Motor Function Measure-32; MIP = maximal inspiratory pressure; NA = not applicable; P0.1 = inspiratory occlusion pressure at 0.1 seconds; PedsQL = Pediatric Quality of Life Inventory; PGIS-I = Parental Global Impression of Secretion Improvement; PGIS-S = Parental Global Impression of Secretion Severity.

^a All inclusion/exclusion criteria should be reviewed on Day -1 to confirm that the subject continues to meet eligibility criteria before dosing.

^b Baseline measures of medical history, physical examination, vital signs, and assessment of ventilator use should be collected on Day -1. Medical history at baseline should capture changes since the screening visit.

^c Complete physical examination at Baseline. At all other timepoints, conduct an abbreviated physical examination based on the subject's circumstances and in accordance with the Investigator's clinical judgement.

^d Record whether the subject was on or off of ventilatory support when vital signs are taken.

^e ECHOs should include an assessment of pulmonary hypertension as well as structural and functional abnormalities. Particular attention should be paid to ECG and ECHO abnormalities specific to myocarditis. Refer to [Section 4.6.1](#) for management of ECG and ECHO results and the role of the site pediatric cardiologist.

^f See [Appendix 1](#) for list of laboratory assessments.

- ^g It is recommended to use the central laboratory to analyze laboratory tests for delayed-treatment control visits. However, the local laboratory can be used if needed (for example, the local laboratory can accommodate the analysis with a smaller amount of blood) or if the local laboratory does not accommodate the appropriate analysis, the central laboratory may be used.
- ^h See [Section 4.6.1](#) for details related to the evaluation of cardiac enzymes; monitoring, diagnosis, and treatment of myocarditis; and the role of the site pediatric cardiologist.
- ⁱ See [Section 4.6.2](#) for details related to the monitoring, diagnosis, and treatment of hepatobiliary toxicity and the role of the site hepatologist.
- ^j Subjects in Germany will not have a wrist X-ray.
- ^k The diary should be completed daily by the same parent/LAR/caregiver (whenever possible); see [Section 5.1.1.11.2.1](#).
- ^l The site pulmonologist and local pulmonologist, if applicable, will review the results from the visit, assess the subject, determine if the subject meets the criteria outlined in [Table 1](#) to begin reduction of hours on the ventilator, and determine if the subject meets the criteria outlined in [Table 2](#) to discontinue the ventilator.
- ^m The severity of secretions and burden of secretions management will be assessed using the PGIS-S and PGIS-I ([Appendix 3](#)). The same parent/LAR/caregiver should report throughout the study (whenever possible).
- ⁿ At baseline, the PGIS-S is conducted for all subjects.
- ^o All physical therapy assessments should be videoed and performed according to the site manual.
- ^p The PedsQL is to be performed for all subjects, regardless of age. Subjects < 2 years of age should be administered the version for 2- to 4-year-olds.
- ^q See [Appendix 5](#). At baseline, only the CGI-S is conducted for all subjects.
- ^r Parents/LARs/caregivers (the same person every time, whenever possible) in ASPIRO will be asked to complete forms for subjects 8 months and older.

5.8 Unscheduled Visits

Additional assessments and optional assessments conducted as part of the study should be recorded on the unscheduled visit eCRFs.

5.9 Assessments for Early Withdrawal from Study

If a subject chooses to withdraw from the study, every attempt should be made to perform the early withdrawal procedures as listed for Week 48 in [Section 5.5](#) for treated subjects and for Control Week 48 in [Section 5.7](#) for control subjects. Medical and public records and/or laboratory results should continue to be obtained once the subject has withdrawn consent for safety and scientific reporting. Additional details can be found in the CRF Completion Guidelines.

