1.5 Overall Risks and Benefits

Key study risks are listed below:

- Subjects will have study procedure-related risks:
 - **Blood collection:** The risks of venous blood draws include discomfort at the site of puncture, possible bruising and swelling around the puncture site, rarely an infection; and, uncommonly, fainting, nausea, vomiting, and light-headedness from the procedure.
 - **Muscle biopsy:** The muscle biopsy has potential complications from the procedure that include infection at the biopsy site, bleeding and/or pain at the site of the biopsy, and psychological trauma from the scar at the site of the incision; in some cases, keloid formation can increase scarring.
 - **Cardiac or muscle magnetic resonance imaging (MRI):** The MRI scan is not associated with risks unless a subject has certain types of metal implants such as pacemakers.
 - **Procedural sedation risk:** Sedation risks in children with weak respiratory muscles varies with the medication used. Sedation risks will be explained to the family. Sedation for the imaging must be carefully administered in patients with XLMTM, since most anesthetic agents act directly on the muscle. Bulbar dysfunction, respiratory muscle weakness, gastroesophageal reflux, and scoliosis increase the risk of pneumonia. Children with respiratory and bulbar muscle weakness who are not ventilator dependent may require invasive or noninvasive ventilation after the procedure. The duration of increased ventilatory requirements would vary depending on the degree of respiratory muscle weakness. The potential side effects of specific medications administered for sedation (eg, vomiting, respiratory depression, laryngospasm, emergence reaction), and the likely duration of sedation will be discussed during informed consent for the procedure.
 - **Prophylaxis (prednisolone, ursodiol):** Subjects receive prophylactic prednisolone and ursodiol as part of the clinical study. Information regarding the risks associated with these medications can be found in the respective local prescribing information.
- Overall risks associated with rAAV gene therapy administration include hepatotoxicity, cardiac events such as myocarditis, myositis, thrombocytopenia, thrombotic microangiopathy (TMA), and sensory ganglionopathy ([Arjomandnejad, 2023](#); [FDA, 2021](#); [Lek, 2023](#); [Shen, 2022](#); [Whiteley, 2023](#)).

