 - *Chronic cardiac risks:* Following prolonged immunosuppression for over 3 years, 1 subject experienced an increase in cardiac troponin levels after withdrawal of immunosuppression. Abnormalities in cardiac function have not been observed in this subject. However, long term assessment is required to understand whether there could be more significant impact on cardiac function.
- **Muscle abnormalities:** A skeletal muscle immune response to the rAAV capsid and to the transgene can occur after rAAV gene therapy administration.
 - *Acute and subacute creatine kinase (CK) elevations:* In Study ATX-MTM-002, variable increases in CK levels after AT132 administration were commonly observed, occurring soon after dosing. These CK levels generally returned to normal within the first year after AT132 administration.
 - *Chronic CK elevations and inflammatory infiltrates in skeletal muscles:* Assessment of muscle biopsies demonstrated treatment-associated inflammatory changes in muscle biopsy specimens of some subjects. No SAEs were reported in association to these findings. Improvements in neuromuscular function (respiratory and motor) have been maintained. Although the CK levels generally returned to normal within the first year after AT132 administration, chronic CK elevation over several years can occur.
- **Thrombocytopenia:** Subjects may develop transient thrombocytopenia or decreases in platelet levels from baseline after AT132 administration. In Study ATX-MTM-002, transient thrombocytopenia related to AT132 occurred within the first 2 weeks of dosing (Shieh, 2023).

Key potential study benefits include the following:

- Independent of efficacy, study subjects may receive better-coordinated and more comprehensive overall clinical care at centers of excellence.
- AT132, even if only partially effective, could cause clinically important improvements in respiratory function and mobility and a lowered risk of disease-related comorbidities, leading to greater independence for the subject and caregivers.
- Other patients may benefit from knowledge gained about XLMTM.

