3.5.2 Withdrawal Follow-Up Procedures

The Investigator will make every reasonable effort to complete the protocol-specified follow-up procedures as specified in [Section 5.9](#), including the follow up of any unresolved AEs as described in [Section 6.1.3.2](#). See [Section 5.10](#) for a description of assessments for delayed-treatment control subjects who are not eligible to be dosed.

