5.1.1.26 Muscle Biopsy (Quantitative Assessment of Tissue Changes)

Muscle biopsies will be collected using a standard muscle open biopsy protocol. Preference of muscles to biopsy will be (1) left gastrocnemius; (2) right gastrocnemius; and (3) vastus lateralis (either side). A different muscle may be biopsied if imaging studies (eg, muscle MRI) suggest a higher probability of muscle tissue collection in another muscle group (eg, biceps brachii).

Muscles that have been biopsied previously will not be re-biopsied during this study to avoid the potential for sampling of the old biopsy site. Biopsy sites will be taken from the target muscle at least 3 cm away from myotendinous insertion sites and sites of known prior muscle injections or electromyography needle sites.

Muscle biopsies will be used to assess the efficacy and safety of AT132 by analyzing MTM1 protein expression, vector copy number quantitation, RNA transcripts assessment, histological characterization and inflammatory markers.

If a muscle biopsy is performed at the discretion of the investigator for diagnostic purposes, including but not limited to CK elevations and declining neuromuscular function

([Section 4.6.3.2](#)), testing should be performed in accordance with standards of care for diagnostic muscle biopsy assessment.

When possible after diagnostic muscle biopsy, muscle should be collected and sent to the central lab for the AT132-related assessments listed below:

- MTM1 protein expression
- Vector copy number quantitation
- RNA transcript assessment
- Histological characterization
- Inflammatory markers

Automatic muscle specimen segmentation techniques will be used to assess pathological features (eg, myofiber size, internally/centrally nucleated myofibers) using machine learning, computer vision techniques, and algorithms that have been developed to measure challenging skeletal muscle specimens ([Liu, 2013](#); [Liu, 2014](#); [Liu, 2015](#)) and further adapted for XLMTM tissue. Muscle specimens will be processed by the clinical study site and sent to a Sponsor designated central reader for review. Details will be provided in a separate procedure manual.

If a subject had a diagnostic biopsy prior to study enrollment, it will not be eligible for use as the pre-treatment biopsy due to concerns about variable tissue handling procedures and age-related changes in pathology.

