Study Phase/Visit	Daily	Weeks 9, 10, 11	Week 12	Weeks 13, 14, 15	Week 16	Weeks 20, 28, 32, 40, 44	Week 24	Week 36	Week 48 or Early Withdrawal	Month 15	Months 18, 24, 30, 36, 42	Months 48, 54, 60
Study Day(s)	NA	63, 70, 77	84	91, 98, 105	112	140, 196, 224, 280, 308	168	252	336	456	548, 730, 913, 1095, 1278	1460, 1643, 1825
Visit Window (days)	-1	±3	±3	±3	+10	±3	±14	±14	±14	±14	±14	±14
ACEND			X		X		X	X	X		X	X
PedsQL ^x			X		X		X	X	X		X ^{ff}	
Clinical global impression scales ^y			X		X		X	X	X		X	X
In-depth interviews with caregiver and subject ^z							X		X			
Swallowing questionnaire			X		X		X	X	X		X	X
Speech questionnaire			X		X		X	X	X		X ^{ff}	
Communicative Development Inventories ^{aa}			X		X		X	X	X		X ^{ff}	
Muscle biopsy							X		X			
Glucocorticoid administration ^{bb}	to Wk 16											
Ursodiol administration ^{cc}	to Wk 12											
Viral shedding (central lab) ^{dd}		Wks 9, 11 only		Wks 13, 15 only			X	X	X		X	X
AEs/concomitant medications		X	X	X	X	X	X	X	X	X	X	X

AEs = adverse events; ACEND = Assessment of Caregiver Experience with Neuromuscular Disease; anti-AAV8 = anti-adenovirus 8; BID = twice daily; CHOP INTEND = Children's Hospital of Philadelphia Infant Test of Neuromuscular Disorders; CK = creatine kinase; ECG = electrocardiogram; ECHO = echocardiogram; ELISpot = enzyme-linked immunosorbent spot assay; IFN-γ = interferon-gamma; IMP = investigational medicinal product; LFTs = liver function tests; MTM1 = gene encoding the myotubularin protein; MEP = maximal expiratory pressure; MFM-32 = Motor Function Measure-32; MIP = maximal inspiratory pressure; NA = not applicable; NAb = neutralizing antibody; ; P0.1 = inspiratory occlusion pressure at 0.1 seconds; PBMCs = peripheral blood mononuclear cells; PedsQL = Pediatric Quality of Life Inventory; PGIS-I = Parental Global Impression of Secretion Improvement; PGIS-S = Parental Global Impression of Secretion Severity; TAb = total antibody; TID = three times a day; WK = week.

NOTE: Week 9, 10, 11, 13, 14, or 15 procedures can be performed at the study site clinic, or in the subject's home by a trained home health nurse. If the home health nurse is utilized then the safety laboratory tests will be sent to the central laboratory for processing. Home health nurses may collect laboratory samples, perform a limited physical examination, vital signs, and review concomitant medications and AEs upon request of the Investigator, as needed at any protocol scheduled visit or unscheduled visit.

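### The early-withdrawal list in Protocol 5.9 has no time limit, so a treated child who leaves years after dosing is still asked for an open muscle biopsy that no visit after Week 48 schedules

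*Protocol*

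**What the plan says.** Protocol 5.9 covers a subject who chooses to withdraw. For treated children, "every attempt should be made to perform the early withdrawal procedures as listed for Week 48" in Section 5.5. Section 3.5.2 points the same way: "The Investigator will make every reasonable effort to complete the protocol-specified follow-up procedures as specified in" Section 5.9. Neither gives a latest time. Section 3.5.1 allows withdrawal at any time, and follow-up runs for 10 years after dosing.

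The column concerned in Section 5.5 is headed "Week 48 or Early Withdrawal". The row "Muscle biopsy" is marked in it. Section 5.1.1.26 describes the procedure: "Muscle biopsies will be collected using a standard muscle open biopsy protocol". It adds that "Muscles that have been biopsied previously will not be re-biopsied during this study", so each further biopsy needs a new muscle.

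Section 1.5 gives the risks: "The muscle biopsy has potential complications from the procedure that include infection at the biopsy site", followed by bleeding, pain and scarring. It describes sedation as a separate risk in children with weak respiratory muscles.

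**The concern.** Read literally, the rule treats leavers and stayers differently for no stated reason. After Week 48 the protocol schedules no biopsy for a child who remains in follow-up, yet the site must try to obtain one from a child whose family is leaving. No clinical finding has to trigger it.

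What is at stake is an avoidable invasive procedure in a young child, with the local complications named in Section 1.5 and, where sedation is used, the respiratory risk as well. Section 1.5 notes that weak children who do not depend on a ventilator may need ventilation after sedation, which could include children weaned after treatment. A biopsy with a clinical reason already has its own route in Section 4.6.3.2, and Section 5.1.1.26 asks for that tissue to go to the central laboratory when possible.

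**Working it through.** The check sets the schedules side by side. The only arithmetic is on study days and document dates.

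**1. Where the biopsy row is marked for treated children**

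| Schedule | Biopsy marked |
|---|---|
| 5.4 (Biopsy visit to Week 8) | Once, before dosing (by Day -6) |
| 5.5 (Week 9 to Month 60) | Week 24; Week 48 or early withdrawal |
| 5.5, Month 15, Months 18–42, Months 48–60 | Blank |
| 5.6 (Month 72 to Month 120) | No biopsy row and no withdrawal column |

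Scheduled biopsies: 1 + 1 + 1 = 3. For a child who had all three, a late exit biopsy would be the fourth. The control schedule in 5.7 has no biopsy row, so the point concerns treated children only.

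**2. Length of the gap**

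The last scheduled biopsy is at Day 336 and the last visit at Day 3650. 3650 − 336 = 3314 days, and 3314 / 365.25 ≈ 9.1 years. Over that span no biopsy is scheduled, but 5.9 still calls for one at withdrawal.

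**3. Whether any text limits the request**

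- Sections 3.5.1, 3.5.2, 5.1.1.26, 5.2 and 5.9 contain no time limit on the early-withdrawal list.
- Footnotes ee and ff of 5.5 stop several assessments from Month 48. Neither is attached to the biopsy row.
- The column heading could be read as covering only exits before Week 48, but neither 5.9 nor the table says so. Footnote d of 5.5 pairs Month 60 with early withdrawal for the complete physical examination, which shows the term is not confined to the first 48 weeks.

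**4. Who the request can still reach**

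Inputs: v10, which stopped dosing, is dated 03 Feb 2022, and v12 is dated 17 May 2024 (version list in the summary of changes). Week 48 is Day 336 ± 14 (Section 5.5). Assumption: no dosing after the v10 date.

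- v10 to v12: 834 days; 834 / 30.4375 = 27.4 months.
- With dosing as Day 1, the most recently dosed child was at Day 834 + 1 = 835 or later at v12.
- End of the Week 48 window: 336 + 14 = Day 350.
- Margin: 835 − 350 = 485 days.

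Range for the assumption: the conclusion holds for any last dosing date up to 17 May 2024 − 350 days = 02 Jun 2023, which is 484 days after v10. Within that range no treated child could still withdraw before or during the Week 48 window once v12 was in force, so the biopsy request is left with late exits only.

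**The case against.** The strongest reply is that the request passes through several filters. It is best effort. Section 3.5.1 limits collection to what is feasible and agreed. The families concerned are already leaving. Section 5.2 allows assessments after Month 60 to be remote at the investigator's discretion, and an open biopsy cannot be done remotely. Section 1.4.2 puts the first six low-dose children at least 2 years past dosing on 08 July 2020. Any of them still followed at v12 were therefore about 5.9 years or more past dosing, beyond Month 60. With no dosing after v10, every remaining child passes Month 60 by about February 2027. All of this stands and makes the expected harm small. It does not remove the instruction: Section 5.2 does not mention the withdrawal list, and a site that follows 5.9 literally must still try. The CRF Completion Guidelines, which 5.9 cites and which are not available here, might narrow the list.

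A late sample also has a plausible safety use. Section 5.1.1.26 gives biopsies a safety purpose, and Section 1.5 reports: "Assessment of muscle biopsies demonstrated treatment-associated inflammatory changes in muscle biopsy specimens of some subjects". That stands as a real cost of the change. That the Week 24 endpoint does not need a late biopsy settles little, because it does not need the Week 48 biopsy either.

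A reader might go further and infer that a late exit biopsy would serve no analysis, because SAP Table 9 has no biopsy window. The documents do not support that. SAP 4.4.2.2.4 summarizes myotubularin expression by visit, plots it over time and lists it, and SAP 4.7.1.2 lists all available vector DNA data from biopsies and summarizes them by visit. Table 9 lacks a biopsy window for every visit, including Week 24, so its silence says nothing particular about late exits.

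**Conclusion.** The gap is real and minor. Protocol 5.9, together with the Section 5.5 column, asks for an open biopsy at any withdrawal up to Month 120, although none is scheduled after Week 48. If no child was dosed after v10, or at the latest after 02 Jun 2023, the request now reaches only children leaving late. For a child with all three scheduled biopsies it would be the fourth, from a new muscle.

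The documents give no count of withdrawals, and the number of such biopsies could be zero. The text does not make the biopsy compulsory, and no planned Week 24 analysis depends on it. The case for acting is participant safety at low cost. The main uncertainty is whether the CRF Completion Guidelines already limit the list.

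**What to change.** Add one sentence to Section 5.9 and repeat it as a footnote to the muscle biopsy row in Section 5.5:

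*No muscle biopsy is performed at withdrawal after the Week 48 visit unless clinically indicated under Section 4.6.3.2.*

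Leave the rest of the early-withdrawal list as it is. Replacing it with the Section 5.6 schedule would drop vital signs, ECG, ECHO, antibody tests and viral shedding, which are worth having at exit. Nothing need be added for the assessments under footnotes ee and ff, because the v12 text already stops them from Month 48.

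The cost is one sentence and one footnote at the next amendment. A few late tissue results may be lost, including inflammatory-marker data from children without a clinical trigger. The diagnostic route keeps biopsy available where there is a clinical reason.
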